1.0 PROTOCOL SYNOPSIS

1.1 Background and Significance

The new water gradient DAILIES TOTAL1 daily disposable contact lens has been touted as a “revolution” in the evolution of contact lens design with the promise of enhancing comfort, a consistent barrier to the global growth of the contact lens market. With the silicone core and six micron thick hydrophilic surface gel, this lens is designed to mimic the ocular surface and increase lubricity while maintaining optimal oxygen permeability. While all types of contact lens wear have been shown to alter the normal homeostasis of the corneal epithelium resulting in a decrease in apoptotic-mediated surface cell shedding and a corresponding increase in size of surface cells, the cellular impact of the water gradient DAILIES TOTAL1 has not yet been established. The goal of this study is to evaluate the effects of the DAILIES TOTAL1 on the biology of corneal epithelium over two months of daily wear compared to wear of a high oxygen permeable silicone hydrogel daily disposable contact lens, the ACUVUE TruEye; and to correlate these changes with alterations in the lid wiper, tear film and cellular changes at the limbus.

1.2 Test Hypotheses

This proposal will test the primary hypothesis that:

- A. The magnitude of the reduction in corneal epithelial surface cell exfoliation following wear of the new DAILIES TOTAL1 water gradient lens will be less than the magnitude of the reduction measured following wear of a control, high oxygen permeable silicone hydrogel daily disposable contact lens.

This proposal will test the secondary hypothesis that:

[figure not shown]
- A. The area of corneal surface epithelial cells will not be increased over baseline following wear of the new DAILIES TOTAL1 water gradient lens while the area of corneal surface epithelial cells will be increased following wear of a control, high oxygen permeable silicone hydrogel daily disposable contact lens.

This proposal will test the following exploratory hypotheses:

- A. There will be an improvement in the biology of the lid wiper region following wear of the new DAILIES TOTAL1 water gradient lens when compared to a control, high oxygen permeable silicone hydrogel daily disposable contact lens.
- B. Surface area of limbal epithelial cells will be unchanged following wear of the new DAILIES TOTAL1 water gradient lens, whereas area will be increased following wear of a control, high oxygen permeable silicone hydrogel daily disposable contact lens.

- C. Limbal and central epithelial thickness will be unchanged following wear of the new DAILIES TOTAL1 water gradient lens, whereas thickness will be reduced following wear of a control, high oxygen permeable silicone hydrogel daily disposable contact lens.
- D. Dendritic cell infiltration in the limbal region will be unchanged following wear of the new DAILIES TOTAL1 water gradient lens, whereas dendritic cell infiltration will be increased following wear of a control, high oxygen permeable silicone hydrogel daily disposable contact lens.
- E. Extracellular DNA content of tear fluid will be unchanged following wear of the new DAILIES TOTAL1 water gradient lens, whereas DNA content will be increased following wear of a control, high oxygen permeable silicone hydrogel daily disposable contact lens.

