1.3 Protocol Overview

2.0 SPECIFIC OBJECTIVES

1. The primary experimental objective of this study is to characterize the effect of the DAILIES TOTAL1 compared to a control, high oxygen permeable silicone hydrogel daily disposable contact lens, the ACUVUE TruEye, on corneal epithelial cell desquamation. This effect will be assessed using a standardized ocular irrigation technique to measure:
 - a. Rate of desquamation of corneal epithelial cells (cells/min).
2. The secondary experimental objective of this study is to evaluate the effect of wear of the DAILIES TOTAL1 on the central corneal epithelium compared to a control, high oxygen permeable silicone hydrogel daily disposable contact lens, the ACUVUE TruEye. This effect will be assessed using IVCN to measure:
 - a. Area of surface epithelial cells within the central cornea (μm^2).
3. Multiple exploratory aims will also be investigated. These aims will be used to evaluate the effects of lens wear on the biology of the corneal and limbal epithelium, lid wiper and changes in the extracellular tear content of DNA in response to wear of the DAILIES TOTAL1 compared to a control, high oxygen permeable silicone hydrogel daily disposable contact lens, the ACUVUE TruEye. These will be assessed by:
 - a. Area of surface epithelial cells within the limbal region.
 - b. Dendritic cell infiltration in the limbal region.
 - c. Staining of the lid wiper region with sodium fluorescein and lissamine green.
 - d. IVCN evaluation of the eyelid.
 - e. Quantification of extracellular DNA adherent to the posterior lens surface and in the post lens tear film.

Detailed descriptions of the study design, procedures, data management and human protection are provided in the following sections.

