3.0 STUDY DESIGN

3.1 Overview

This is a prospective, single center, randomized, bilateral crossover, dispensing clinical trial to evaluate the effects of the water gradient lens, DAILIES TOTAL1, on the biology of corneal epithelium over two months of daily wear compared to wear of a control high oxygen permeable silicone hydrogel daily disposable contact lens, the ACUVUE TruEye; and to correlate these changes with alterations in the lid wiper, tear film and cellular changes at the limbus. The total proposed duration of this study is 12 months to ensure enrollment of up to 140 established contact lens wearers, with anticipated completion of 84. Data will be collected at

baseline and following 2 months of daily wear for each lens type. Based upon data from our previous contact lens clinical trials, a 1 month washout period is required prior to initiating lens wear to eliminate any potential residual solution or lens effects on the corneal epithelium and restore homeostasis. The study is scheduled to commence upon IRB approval.

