3.4.4 Sample Size Determination and Statistical Methods

A total of 140 patients will be recruited for this study. Sample size calculations (detailed below) and statistical methods to detect significant changes in the outcome measures were derived from our previous studies evaluating the effects of silicone hydrogel lens wear on the corneal epithelium (Ladage et al, *Ophthalmology* 2001; 108: 1279-1288 and Robertson et al, *IOVS* 2008; 49: 7-15). The magnitude of change for of all outcome measures will be simultaneously compared between lens types using a Type I error rate of $\alpha=0.05$. Statistical analysis will be completed in the Department of Clinical Sciences and Biostatistics at UTSWMC.

A. Surface epithelial cell desquamation

Surface epithelial cell desquamation is the most sensitive and reliable predictor of epithelial perturbation in response to contact lens wear. In our prior studies, silicone hydrogel lens wear worn in a daily modality reduced corneal surface epithelial cell desquamation by 40-50%. We hypothesize that the impact on epithelial shedding rate (cells/minute) will be less following wear of the Dailies Total 1 ($\Delta \leq 20\%$ reduction) compared to wear of a standard silicone hydrogel daily disposable, the ACUVUE TruEye ($\Delta \geq 40\%$ reduction). Assuming a difference in means between the two test lenses of 16.3 cells/minute and a standard deviation of 37 cells/minute, a total sample of 84 subjects in a 2x2 cross-over design will have 80% power at a significance level of $\alpha=0.05$.

B. Drop outs

Additional subjects were added to compensate for the potential dropouts to satisfy the requirements for completion of the 6 month study. Based upon our previous clinical trials, we anticipate a dropout rate of 10-12%. In the absence of time, cost, and ethical concerns, Guo et al. (2013) suggested choosing the largest sample size to guarantee power for all 2 tests. Therefore, we will recruit a total of 94 subjects for this cross-over trial. That is, 47 subjects will be allocated to each sequence in this 2x2 cross-over trial.

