6.4 Data Analysis Procedures

Data analysis will begin with the extraction of data from the master database in ophthalmology. Range and validity checks and determination of validity of missing values will be a first step in analysis. Patient confidentiality will be assumed during data analysis in that the patient names will not be used but will be numerically coded. Data will be analyzed using an intent-to-treat approach.

Continuous demographic and baseline characteristics will be compared between the DAILIES TOTAL1 and the ACUVUE TruEye using Student's t-tests or Wilcoxon rank sum tests. Categorical demographic and baseline characteristics will be compared between the DAILIES TOTAL1 and the ACUVUE TruEye using Fisher's exact tests or Chi-square tests.

Data analysis will be specific to the objectives outlined below:

1. The primary experimental objective of this study is to characterize the effect of the DAILIES TOTAL1 compared to a control, high oxygen permeable silicone hydrogel daily disposable contact lens, the ACUVUE TruEye, on corneal epithelial cell desquamation. This effect will be assessed using a standardized ocular irrigation technique to measure:
 - a. Rate of desquamation of corneal epithelial cells (cells/min).

In this cross-over trial, treatment effects and carryover effects on the rates of desquamation of corneal epithelial cells (cells/min) will be compared between two treatment groups using Student's t-tests in Rosner (2006), and ANOVA in Chow and Liu (2014). If the p-value is less than $\alpha=0.05$ for surface epithelial cell desquamation, then the surface epithelial cell desquamation is considered significantly different between the two groups.

References:

Rosner B. (2006) Fundamentals of Biostatistics, 6th Edition. Thomson-Brooks/Cole.

Chow S and Liu J. (2014) Design and analysis of clinical trials: concepts and methodologies, 3rd Edition. Wiley.

2. The secondary experimental objective of this study is to evaluate the effect of wear of the DAILIES TOTAL1 on the central corneal epithelium compared to a control, high oxygen permeable silicone hydrogel daily disposable contact lens, the ACUVUE TruEye. This effect will be assessed using IVCN to measure:
 - a. Area of surface epithelial cells within the central cornea (μm^2).

Same analytical methods as described above for the primary endpoint will be used for the analysis of the secondary endpoint.

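### The secondary hypothesis makes two within-lens claims about surface cell area, but the only planned test compares the lenses and can establish neither claim

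*Combined protocol and SAP*

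**What the plan says.** **Hypothesis.** Section 1.2 names two things the trial will test. One is "The area of corneal surface epithelial cells will not be increased over baseline following wear of the new DAILIES TOTAL1 water gradient lens". The other is that area does rise with the control. The primary hypothesis in the same section is worded differently: it says the reduction in exfoliation will be smaller with one lens than with the other.

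**Objective.** Section 2.0 frames the secondary aim as a comparison: to "evaluate the effect of wear of the DAILIES TOTAL1 on the central corneal epithelium compared to a control" lens, measured by central surface cell area. Section 6.4 repeats this.

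**Analysis.** Section 6.4 compares treatment and carryover effects on desquamation between the two lens groups with t-tests and ANOVA at 0.05. For cell area it then says "Same analytical methods as described above for the primary endpoint will be used for the analysis of the secondary endpoint". Section 3.4.4 agrees: "The magnitude of change for of all outcome measures will be simultaneously compared between lens types".

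**Data.** Section 3.1 has measurements taken at "baseline and following 2 months of daily wear for each lens type". Section 3.2 lists confocal microscopy at Visits 2, 4, 5 and 7.

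**Sample size.** Section 3.4.4 gives one calculation, for desquamation. Under drop-outs it also cites a suggestion of "choosing the largest sample size to guarantee power for all 2 tests". It does not say which two tests are meant.

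**The concern.** Each half of the secondary hypothesis concerns the change on one lens from its own baseline. The planned test concerns the difference between the two changes. A difference can be real when both lenses enlarge cells, when neither does, or when one shrinks them, so a significant result does not say which of these happened.

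The case of most interest is plausible on the protocol's own account. Section 1.1 says that all types of lens wear have been shown to enlarge surface cells. If DAILIES TOTAL1 enlarges them somewhat and the control enlarges them more, the between-lens test may correctly be significant. With the hypothesis worded as it is, that result could be reported as confirming that DAILIES TOTAL1 causes no increase, which would be false.

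**Working it through.** **1. The plan's own figure.** Section 3.4.4 gives a difference of 16.3 cells/min, an SD of 37, alpha 0.05 and 84 completers in a 2x2 crossover. Taking 37 as the within-subject SD, the SD of the paired difference is 37 × √2 = 52.3. The noncentrality is 16.3 / (52.3/√84) = 2.86. With 82 df and a two-sided 0.05 test, power is 80.6%; at 82 subjects it is 79.6%. So 84 reproduces, and it supports the between-lens test on desquamation. Nothing comparable is given for cell area.

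**2. What the planned test can see.** Let T and C be the true mean changes on DAILIES TOTAL1 and the control. The hypothesis says T ≤ 0 and C > 0. The test statistic depends on C − T alone.

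The documents give no effect, SD, correlation or margin for cell area. All inputs below are therefore assumptions, in units of the SD of within-lens change, with 84 completers.

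Simulated chance of a significant lens difference, changes independent between periods:

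| T | C | Hypothesis | Significant |
|---|---|---|---|
| 0 | +0.5 | true | 89% |
| +0.5 | +1.0 | DAILIES TOTAL1 half false | 89% |
| −0.5 | 0 | control half false | 90% |

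The result does not separate the three situations.

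**3. Both lenses enlarge cells.** Take T = 0.3 and C = 0.7, a gap of 0.4. The SD of the difference is √(2(1 − ρ)), where ρ is the correlation between the two changes. Noncentrality is 0.4 × √84 / √(2(1 − ρ)), with 82 df, two-sided 0.05.

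| ρ | SD of difference | Noncentrality | Power |
|---|---|---|---|
| 0 | 1.414 | 2.59 | 72.6% |
| 0.3 | 1.183 | 3.10 | 86.5% |
| 0.5 | 1.000 | 3.67 | 95.2% |

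The lenses truly differ and the test usually says so, yet the no-increase claim is false.

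**4. Would an unplanned within-lens test repair this?** Not through a non-significant result. Noncentrality is the true rise × √84, with 83 df.

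| True rise (SD) | Missed, two-sided 0.05 | Missed, one-sided 0.05 |
|---|---|---|
| 0.1 | 85.2% | 76.9% |
| 0.2 | 55.9% | 43.1% |
| 0.3 | 22.4% | 14.0% |

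The pattern most easily read as confirmation is a significant lens difference with no significant DAILIES TOTAL1 rise, each tested two-sided at 0.05. In 200,000 simulated trials with normal changes, no period effect and ρ from 0 to 0.5, it occurs in about 22% of trials when the rises are 0.3 and 0.7 SD. It occurs in 50% to 55% when they are 0.2 and 0.6 SD. The no-increase claim is false in both settings.

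**5. What a margin would need.** The half-width of a 95% interval for one lens's mean change is t(0.975, 83)/√84 = 0.217 SD. With a true change of zero, the chance that the upper limit falls below the margin is 44.1% at 0.2 SD, 77.6% at 0.3, 80.2% at 0.31 and 95.2% at 0.4.

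**The case against.** The strongest reply is that objective and analysis agree, and only the hypothesis sentence is out of line. No planned estimate or test is wrong. Section 6.4's sole decision rule is a significant difference between groups, so nothing in the plan licenses a conclusion of no increase. On this view it is a wording slip, and its harm depends on a later misreading.

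Much of that stands. The test should be kept, and the primary endpoint is untouched. But section 1.2 says the trial will test these claims, and no stated analysis does so. The primary hypothesis shows that a fitting form of words was available.

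A second reply is that the miss rates and joint patterns in step 4 concern a within-lens test the plan does not contain, on invented inputs. That is fair. They show only that the obvious improvised repair would not work. The structural point needs none of these numbers.

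Third, the remark about two tests in section 3.4.4 is a separate and minor matter: the only calculation is already headed as desquamation. It merits one clarifying sentence and is not part of the main argument.

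The exploratory hypotheses have similar wording, but section 6.4 plans only exploratory and descriptive analysis for them, so they need less.

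**Conclusion.** The concern holds. As written, the secondary hypothesis cannot be established by the planned analysis: the claims are within-lens, the test is between-lens, and no margin or interval rule connects them. This follows from the text and does not depend on any assumed value.

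The size is illustrative only. With assumed rises of 0.3 and 0.7 SD, the planned test would be significant in 73% to 95% of trials although the claim of no increase is false. Those figures rest on 84 completers and correlations of 0 to 0.5. The point should be corrected, but it concerns the secondary endpoint only. The primary hypothesis, its analysis and the sample size of 84 completers are not affected.

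**What to change.** - **Section 1.2.** Restate the secondary hypothesis as: the rise in central surface cell area from baseline is smaller with DAILIES TOTAL1 than with ACUVUE TruEye. This fits both the objective and the test.
- **Section 6.4.** Keep the between-lens test. Add a sentence to report each lens's mean change from its own period baseline (Visits 2 and 5) with a 95% confidence interval. If a claim of no increase is still wanted, allow it only when the upper limit for DAILIES TOTAL1 lies below a margin in μm² fixed before unmasking.
- **Section 3.4.4.** State that the sample size rests on desquamation alone.

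**Cost.** One reworded hypothesis and two added sentences, with no new data, visits or subjects. The secondary claim and the power statement become more modest. The margin is optional and would need a biological justification that the documents do not supply. With 84 completers and no true change, it would have to be at least about 0.31 SD of within-lens change for an 80% chance of meeting it.

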1.3 Protocol Overview

2.0 SPECIFIC OBJECTIVES

1. The primary experimental objective of this study is to characterize the effect of the DAILIES TOTAL1 compared to a control, high oxygen permeable silicone hydrogel daily disposable contact lens, the ACUVUE TruEye, on corneal epithelial cell desquamation. This effect will be assessed using a standardized ocular irrigation technique to measure:
 - a. Rate of desquamation of corneal epithelial cells (cells/min).
2. The secondary experimental objective of this study is to evaluate the effect of wear of the DAILIES TOTAL1 on the central corneal epithelium compared to a control, high oxygen permeable silicone hydrogel daily disposable contact lens, the ACUVUE TruEye. This effect will be assessed using IVCN to measure:
 - a. Area of surface epithelial cells within the central cornea (μm^2).
3. Multiple exploratory aims will also be investigated. These aims will be used to evaluate the effects of lens wear on the biology of the corneal and limbal epithelium, lid wiper and changes in the extracellular tear content of DNA in response to wear of the DAILIES TOTAL1 compared to a control, high oxygen permeable silicone hydrogel daily disposable contact lens, the ACUVUE TruEye. These will be assessed by:
 - a. Area of surface epithelial cells within the limbal region.
 - b. Dendritic cell infiltration in the limbal region.
 - c. Staining of the lid wiper region with sodium fluorescein and lissamine green.
 - d. IVCN evaluation of the eyelid.
 - e. Quantification of extracellular DNA adherent to the posterior lens surface and in the post lens tear film.

Detailed descriptions of the study design, procedures, data management and human protection are provided in the following sections.

3.0 STUDY DESIGN

3.1 Overview

This is a prospective, single center, randomized, bilateral crossover, dispensing clinical trial to evaluate the effects of the water gradient lens, DAILIES TOTAL1, on the biology of corneal epithelium over two months of daily wear compared to wear of a control high oxygen permeable silicone hydrogel daily disposable contact lens, the ACUVUE TruEye; and to correlate these changes with alterations in the lid wiper, tear film and cellular changes at the limbus. The total proposed duration of this study is 12 months to ensure enrollment of up to 140 established contact lens wearers, with anticipated completion of 84. Data will be collected at

baseline and following 2 months of daily wear for each lens type. Based upon data from our previous contact lens clinical trials, a 1 month washout period is required prior to initiating lens wear to eliminate any potential residual solution or lens effects on the corneal epithelium and restore homeostasis. The study is scheduled to commence upon IRB approval.

3.2 Study Workflow

Visit 1: Comprehensive ocular examination (Contact Lens Clinic at UTSW)

- a. Informed consent reviewed and signed
- b. Comprehensive examination
- c. Back-up glasses ordered as needed
- d. Lens fitting and ordering based on randomization into the following lens groups:
 - i. Alcon DAILIES TOTAL1
 - ii. Johnson and Johnson ACUVUE TruEye
- e. One month washout begins immediately or after the participant obtains the spectacles.

Visit 2: Baseline Visit, lens 1 dispensed (+/- 3 days)

- a. Brief screening exam
- b. Informed consent re-reviewed
- c. Baseline biological indicators (outcome measures) assessed
 - i. Tear collection OU
 - ii. Lid wiper staining OD
 - iii. Ocular irrigation OS
 - iv. Confocal microscopy of cornea, limbus and lid margin OD
- d. Lenses dispensed

Visit 3: 1 week of lens wear (+/- 3 days)

- a. Contact lens check up
 1. Snellen Visual Acuity Testing
 2. Lens fitting
 3. Slit lamp examination without corneal staining

Visit 4: 2 month of lens wear (+/- 3 days)

- a. Brief screening exam
- b. Lenses and diaries collected
- c. Biological indicators assessed
 - i. Lenses collected OU
 - ii. Tear collection OU
 - iii. Lid wiper staining OD
 - iv. Ocular irrigation OS
 - v. Confocal microscopy of cornea, limbus and lid margin OD
- d. Patient begins next 1 month washout period

Visit 5: Baseline visit, lens 2 dispensed (+/- 3 days)

- a. Brief screening exam
- b. Baseline biological indicators assessed
 - i. Lenses collected OU
 - ii. Tear collection OU
 - iii. Lid wiper staining OD
 - iv. Ocular irrigation OS
 - v. Confocal microscopy of cornea, limbus and lid margin OD
- c. Lenses dispensed – begin crossover phase

Visit 6: 1 week of lens wear (+/- 3 days)

- a. Contact lens check up
 - i. Snellen Visual Acuity Testing
 - ii. Lens fitting
 - iii. Slit lamp examination without corneal staining

Visit 7: 2 month of lens wear (+/- 3 days)

- a. Brief screening exam
- b. Lenses and diaries collected
- c. Biological indicators assessed
 - i. Lenses collected OU
 - ii. Tear collection OU
 - iii. Lid wiper staining OD
 - iv. Ocular irrigation OS
 - v. Confocal microscopy of cornea, limbus and lid margin OD
- d. Study completed

Table 1: Overall study design

Visit No.	Interval	Time in lens	Procedures
1	0	0	Sign and review IC. Comprehensive ocular examination. Order back-up glasses if needed. Lens fitting and ordering. One month washout period of no lens wear.
2	1 month	0	Brief screening exam. Informed consent re-review. Baseline biological indicators assessed. Dispense contact lenses.
3	1 month, 1 week	1week	Contact lens check.
4	3 months	2 months	Lenses and diaries collected. Biological indicators assessed. Begin next washout period.
5	4 months	0	Baseline biological indicators assessed. Lenses dispensed.

6	4 months, 1 week	1 week	Contact lens check.
7	6 months	2 months	Lenses and diaries collected. Biological indicators assessed. Study completed.

